10.3.1 Evaluable for toxicity

All participants will be evaluable for toxicity from the time of their first treatment with SX-682. Participant will be eligible for the DLT evaluation if at least ≥ 85 percent of SX-682 scheduled doses were taken and 100% of scheduled doses of M7824 or CV301 were administered within the DLT period.

10.3.2 Evaluable for objective response

Only those participants who have measurable disease present at baseline, have received at least one cycle of therapy, and have had their disease re-evaluated will be considered evaluable for response. These participants will have their response classified according to the definitions in section **6.3**. (Note: Participants who receive at least treatment cycle and exhibit objective disease progression prior to the first restaging will also be considered evaluable.)

10.3.3 Evaluable Non-Target Disease Response

Participants who have lesions present at baseline that are evaluable but do not meet the definitions of measurable disease, have received at least one cycle of therapy, and have had their disease re-evaluated will be considered evaluable for non-target disease. The response assessment is based on the presence, absence, or unequivocal progression of the lesions.

10.4 STATISTICAL ANALYSES

10.4.1 General Approach

Following a determination of safety, tolerability, and the MTD in Arms 1 and 2, the fraction of participants who experience a response in each disease-specific cohort of Arm 3 will be reported along with confidence intervals.

10.4.2 Analysis of the Primary Endpoints

The toxicity grades per participant will be tabulated and reported by dose level during dose escalation (Arms 1 and 2). This will also include separate evaluations for the initial monotherapy evaluations preceding the evaluation of the combination at each dose level.

In Arm 3, the fraction of participants who experience a response in each disease-specific cohort will be reported along with 95% two-sided confidence intervals.

10.4.3 Analysis of the Secondary Endpoint(s)

10.4.4 PK evaluations will be performed on participants in both dose escalation Arms (both for single agent SX-682 and the combination of agents); results will be reported using standard descriptive statistics. In Arm 3, separately by cohort, the disease control rate (DCR; CR+PR+SD) will be reported as the fraction of participants who experience this outcome, along with a 95% two-sided confidence interval for each fraction. Progression free survival (PFS) will be calculated using the Kaplan-Meier method, including progressions or death without progression as events. Participants who come off study for reasons other than progression and choose not to participate in optional imaging will be censored in data analysis at the time when they become unfollowable for PFS.

10.4.5 Safety Analyses

The fraction of participants who experience a toxicity, by grade and type of toxicity, will be tabulated per dose level (both single agent and combination of agents) during the Arms 1 and 2 portion of the trial. Participants who take one dose or more of SX-682 will be evaluable for safety.

10.4.6 Baseline Descriptive Statistics

Baseline demographic characteristics will be reported.

10.4.7 Planned Interim Analyses

As indicated in the two-stage designs, the number of responses after 9 or 12 evaluable participants have been treated in the appropriate cohort will be noted and will be used to determine if enrollment to the second stage of accrual may proceed for that cohort.

10.4.8 Sub-Group Analyses

In Arm 3, analyses will be performed separately by histology.

10.4.9 Tabulation of individual Participant Data

None

10.4.10 Exploratory Analyses

All Arms:

- To evaluate response via iRECIST
- To evaluate the effect on immune cell subsets and soluble factors in peripheral blood.
- To evaluate the effect on serum cytokine levels (IL-8, IL-6 and others) in peripheral blood.
- To evaluate the effect on T cell clonality in peripheral blood and tumor samples.
- To evaluate the effect on antigen-specific T cells responses to CEA, MUC1 and the cascade antigen brachyury in peripheral blood.
- To evaluate the effect on antigen-specific T cell responses to CEA, MUC1 and the cascade antigen brachyury in the tumor biopsies.
- To evaluate the presence of lymphocytic infiltrates and other tumor markers as well as to evaluate RNA in situ hybridization for IL-8, TGF- β and other soluble factors in tumor biopsies.
- To evaluate M7824 PK profile in this drug combination
- To evaluate ADA in this drug combination
- To evaluate long term (2 years after completion of treatment) clinical outcomes
- To evaluate CTCs

In Arms 1 and 2 (Dose-Escalations), the following are the parameters will be evaluated, separately per dose level:

- To evaluate ORR per RECISTv1.1

In Arm 3 (Expansions) the following are the parameters will be evaluated, separately per cohort.

- To evaluate changes in circulating free DNA.

Any exploratory evaluations which generate quantitative measures will be done using descriptive statistics including confidence intervals when appropriate. Any statistical tests performed for evaluation of exploratory objectives will be done without formal adjustment for multiple comparisons, but in the context of the number of tests performed.

11 COLLABORATIVE AGREEMENTS

11.1 COOPERATIVE RESEARCH AND DEVELOPMENT AGREEMENT (CRADA)

A CRADA (03153) is in place with Syntrix for the supply of SX-682.

A CRADA (02666) is in place with EMD Serono for the supply of M7824.

A CRADA (02561) is in place with Bavarian Nordic for the supply of CV301.

12 HUMAN SUBJECTS PROTECTIONS

12.1 RATIONALE FOR SUBJECT SELECTION

No individual who meets the criteria for eligibility will be excluded from participation based on their race, ethnicity, gender, or socioeconomic status. Particular attention will be made to acquire a broad and diversified population.

12.2 PARTICIPATION OF CHILDREN

Children (younger than 18 years) will not be included in this protocol due to the limited data on study drugs in children and the different biology of childhood malignancy.

12.3 PARTICIPATION OF SUBJECTS UNABLE TO GIVE CONSENT

Adults unable to give consent are excluded from enrolling in the protocol. However, re-consent may be necessary and there is a possibility, though unlikely, that subjects could become decisionally impaired. For this reason and because there is a prospect of direct benefit from research participation (Section [12.4.2](#)), all subjects will be offered the opportunity to fill in their wishes for research and care, and assign a substitute decision maker on the “NIH Advance Directive for Health Care and Medical Research Participation” form so that another person can make decisions about their medical care in the event that they become incapacitated or cognitively impaired during the course of the study. Note: The PI or AI will contact the NIH Ability to Consent Assessment Team (ACAT) for evaluation to assess ongoing capacity of the subjects and to identify an LAR as needed. .

Please see section [12.5.1](#) for consent procedure.

12.4 RISK/BENEFIT ASSESSMENT FOR ALL PARTICIPANTS

12.4.1 Known Potential Risks

12.4.1.1 Study Drug Risks

Risks include the possible occurrence of any of a range of side effects which are listed in the Consent Document or sections [1.2.2.2](#), [1.2.3.1](#), [1.2.4.1](#) of this protocol document. Frequent monitoring for adverse effects will help to minimize the risks associated with administration of the study agents.

12.4.1.2 Risk of Biopsy

All care will be taken to minimize risks that may be incurred by tumor sampling. However, there are procedure-related risks (such as bleeding, infection and visceral injury) that will be explained fully during informed consent.

12.4.1.3 Risks of local anesthesia and/or light sedation.

Biopsies will be done under local anesthesia and/or light sedation. Potential side effects of sedation include headache, nausea and drowsiness. These side effects usually go away quickly.

12.4.1.4 Risks of contrast dye used in CT scans

There is a chance of developing an allergic reaction from the contrast material, which may cause symptoms ranging from mild itching or a rash to severe difficulty breathing, shock or rarely, death. The contrast material may also cause kidney problems.

For IV contrast: Potential side effects include discomfort when the contrast material is injected, feeling warm, flushed, a metallic taste, or rarely vomiting or nausea.

For oral contrast: Potential side effects include vomiting, nausea, cramping, bloating, constipation or diarrhea after drinking the contrast.

12.4.1.5 Risks of exposure to Ionizing Radiation

This research study involves up to nine (9) CT scans (C/A/P) and up to three (3) CT guided biopsies (optional) collected for research purposes only. Subjects undergoing these scans and optional biopsies collection will be exposed up to 12.3 rem.

The CT scans that participant will get in this study will expose them to the roughly the same amount of radiation as 41 years of background radiation. The risk of getting cancer from the radiation exposure in this study is 1.2 out of 100 (1.2 %) and of getting a fatal cancer is 0.6 out of 100 (0.6 %)

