2.2.2 Screening activities performed after a consent for screening has been signed

The following activities will be performed only after the subject has signed the study consent OR the consent for study #01-C-0129 (provided the procedure is permitted on the study) on which screening activities will be performed. Assessments performed at outside facilities or on another

NIH protocol within the timeframes below may also be used to determine eligibility once a participant has signed the consent.

All screening tests and procedures must be performed within 28 days prior to initiation of study therapy, unless otherwise specified:

- Complete medical history and physical examination (including weight, height, vital signs, and ECOG performance status).
- CT of chest, abdomen and pelvis with contrast (preferred)
- A brain CT
- Clinical laboratory tests (within 16 days prior to enrollment)
 - Biochemical Profile: sodium, potassium, chloride magnesium, phosphorus, bicarbonate, calcium, glucose, BUN, creatinine, ALT, AST, alkaline phosphatase, total protein, albumin, and total and direct bilirubin,.
 - Hematology: complete blood count (CBC) with differential and platelets
 - CD4 (if clinically indicated)
 - TSH, free T4, lipase, amylase
 - Lymphocyte panel (TBNK)
 - Coagulation panel: PT, INR, PTT
 - Urinalysis
 - Serum pregnancy test (β -HCG) for females of childbearing-potential and women < 12 months since the onset of menopause (within 7 days prior to enrollment).
 - HBV, HCV (or HCV viral load if recently completed treatment for HCV), HIV viral load by PCR (within 3 months prior to enrollment).
- Electrocardiogram (EKG) in triplicate

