Subjects on all arms will receive combined treatment with study drugs for up to 2 years (BN-CV301 will be administered for up to 1 year on trial; M7824 and SX-682 will be administered for up to 2 years on trial). Furthermore, after 2 years on treatment with M7824 and/or SX-682, the PI can discuss an additional treatment period with CRADA partners as long as in the opinion of the PI the participant continues to gain clinic benefit and is tolerating the drug regimen. Disease progression should be confirmed with a subsequent scan 4 to 8 weeks later prior to removing a participant from study therapy, unless the participant is clinically progressing or is no longer gaining benefit in the opinion of the investigator. Subjects with evidence of disease progression can remain on treatment beyond radiographic progression if in the opinion of the investigator the subject is benefiting from treatment. For complete list of off treatment criteria, see Section **3.7.2**.

Patients may undergo up to three optional biopsies for research purposes only: at baseline, at first restaging (+/- 1 week) and at time of progression.

Schema 1. Cohort 1, Arm 1

Schema 2. Cohort 1, Arm 2. Combination Dose Escalation Cohort.

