⁸ Participants who are taken off treatment for reasons other than disease progression, will be invited for optional imaging studies every 3 months (+/- 2 weeks) until they experience PD in order to assess PFS. If participants unable to come, participants will be followed by phone or email and outside images will be requested. Participants who opt out of these scans will have their data censored in data analysis at the time they become unfollowable for PFS. After progression and 30 days Safety Follow up visit, participants will be followed by phone or email for long-term clinical outcomes, and further tumor therapy every year for 2 years.

⁹ EKGs will be done in triplicate on screening, before SX-682 administration at baseline and then every two weeks until cycle 6, at EOT and at the safety FU visit.

¹⁰ Biochemical profile: sodium, potassium, magnesium, phosphorus, chloride, bicarbonate, calcium, glucose, BUN, creatinine, ALT, AST, alkaline phosphatase, total protein, albumin, and total and direct bilirubin.

¹¹ Performed every 8 weeks: Lymphocyte panel (TBNK), TSH, Free T4, lipase, amylase, urinalysis, PT/PTT/INR, unless there is a clinical concern that warrants evaluation on a more frequent basis

¹² For women of childbearing potential at screening and baseline serum pregnancy test must be performed, but on day 1 of each cycle and EOT, urine pregnancy test can also be used.

¹³ In Arms 1 and 2, the first restaging will occur 6 weeks after starting treatment (+/- 1 week) and then every eight weeks (+/- 1 week). In Arm 3, restaging will occur every eight weeks (+/- 1 week). In the event of a PR or CR tumor imaging assessments may be performed every 3 months (+/- 2 weeks) at the discretion of the investigator. Tumor assessment should be continued beyond end of treatment in participants who have not experienced PD until they experience PD in order to assess PFS. In addition to a baseline scan, confirmatory scans can also be obtained 4 to 8 weeks following initial documentation of objective response per the discretion of the primary investigator. MRI of chest, abdomen and pelvis (if participant has contradiction to CT).

¹⁴ Brain CT/MRI if there is a history of prior CNS metastasis or there is a concern for CNS involvement.

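### The radiation risk statement caps CT scans at nine, but the protocol's calendar schedules 14 for a participant treated for two years without PR or CR

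*Combined protocol and SAP*

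**What the plan says.** Section 12.4.1.5 sets a ceiling on imaging: "This research study involves up to nine (9) CT scans (C/A/P) and up to three (3) CT guided biopsies (optional". The dose follows: "Subjects undergoing these scans and optional biopsies collection will be exposed up to 12.3 rem". It is equated to "roughly the same amount of radiation as 41 years of background radiation", and the risk is then given: "The risk of getting cancer from the radiation exposure in this study is 1.2 out of 100 (1.2" per cent, with 0.6% for fatal cancer. The section states neither a period nor a dose per procedure.

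The imaging schedule is set elsewhere in the protocol:

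- Section 2.2.2 (screening): "CT of chest, abdomen and pelvis with contrast (preferred".
- Section 3.5, footnote 13: "In Arms 1 and 2, the first restaging will occur 6 weeks after starting treatment (+/- 1 week) and then every eight weeks (+/- 1 week".
- The same footnote: "In Arm 3, restaging will occur every eight weeks (+/- 1 week".
- Section 3.1 (duration): "M7824 and SX-682 will be administered for up to 2 years on trial", with a possible extension by agreement with the CRADA partners.

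Footnote 13 also lets the investigator widen the interval to three months after a PR or CR.

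**The concern.** A figure introduced with an upper limit should cover the most heavily imaged participant who follows the protocol. That participant has prolonged stable disease, remains on treatment for two years, and has no route to the three-monthly interval. If the schedule takes this participant past nine scans, the stated maximum dose and cancer risk are exceeded without any deviation from the protocol, and the error is on the favourable side. This is the protocol's quantified statement of radiation risk, so the scan count feeds directly into the risk-benefit assessment in section 12.4.

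**Working it through.** **Stated figures.** They agree with one another: 12.3 rem / 41 years = 0.30 rem per year; 1.2% / 12.3 = about 0.098% per rem; 0.6% / 12.3 = about 0.049% per rem. A wrong scan count would therefore carry through to every figure in the section.

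**Scheduled C/A/P scans over 104 weeks, 8-weekly throughout.** Brain CT and bone scans are left out, because the stated nine are C/A/P scans.

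- Arms 1 and 2: 1 screening + restaging at weeks 6, 14, ..., 102. Restaging = 1 + (102 - 6)/8 = 13. Total 14.
- Arm 3: 1 screening + restaging at weeks 8, 16, ..., 104. Restaging = 104/8 = 13. Total 14.
- Ninth scan = eighth restaging: week 6 + 7 × 8 = 62 (Arms 1 and 2) or 8 + 7 × 8 = 64 (Arm 3). Five scheduled scans remain.
- Running to week 106, to allow for the two-week lead-in, does not change the count.

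**Can nine be reproduced?**

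- One year: restaging at weeks 6 to 46 or 8 to 48 gives 6, plus screening = 7.
- Response at the first restaging, then every 13 weeks: weeks 6, 19, ..., 97 or 8, 21, ..., 99 give 8, plus screening = 9.
- Response at the second restaging, then every 13 weeks: 1 + 2 + 6 = 9.
- Response at the third restaging: 1 + 3 + 6 = 10. Later responders have 10 to 14.
- Every interval stretched by the one-week window (first scan at week 7 or 9, then every 9 weeks): 12. Every interval shortened by a week: 16 (Arms 1 and 2) or 15 (Arm 3).

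Nine is thus the two-year count for an early responder moved to the reduced schedule.

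**Dose and risk for 14 CTs and 3 biopsies.** The split of the 12.3 rem is not given, so I assume that a biopsy carries *r* times the dose of a CT. Dose per CT = 12.3 / (9 + 3*r*); new total = dose per CT × (14 + 3*r*). Years and risks use the conversions above.

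| *r* (assumed) | rem per CT | Total rem | Background years | Cancer | Fatal cancer | Increase over 12.3 rem |
|---|---|---|---|---|---|---|
| 0 | 1.367 | 19.1 | 63.8 | 1.87% | 0.93% | 56% |
| 1 | 1.025 | 17.4 | 58.1 | 1.70% | 0.85% | 42% |
| 1.5 | 0.911 | 16.9 | 56.2 | 1.64% | 0.82% | 37% |

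**The case against.** The best counter-argument concerns scope. The sentence in 12.4.1.5 ends with a restriction to research purposes. If that governs the scans as well as the biopsies, nine counts research-only procedures and need not match the calendar. This reading is possible but poorly supported. Section 3.1 attaches the same restriction to the three optional biopsies, the next paragraph of 12.4.1.5 speaks generally of the CTs received on study, and no section available for this review labels restaging scans as standard of care. If a split was intended, the section does not state it.

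Other objections stand in part:

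- A reader might infer that every participant has at least 14 scans. The documents do not support that. Early responders may have nine, use of the windows can give 12, and participants who progress early have fewer. Fourteen is the nominal count for two full years without PR or CR.
- A reader might also add confirmatory and post-treatment scans as a matter of course. Response confirmation is discretionary (footnote 13), post-treatment imaging is optional (footnote 8), and a progression scan due at 4 to 8 weeks (section 6.3) can coincide with a scheduled one.
- MRI may replace body CT where CT is contraindicated. That lowers some participants' exposure but not the maximum.
- Nine would cover one year's seven scheduled scans with two to spare, but no one-year limit is stated.
- The consent pages are not in the public document, so it cannot be said that participants were given the same figure.

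**Conclusion.** Nine is not a valid ceiling for the CTs that a participant can receive under this protocol. The scheduled count is 14 in every arm over two years at 8-week intervals, and 12 even when every window is stretched.

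Read as covering all study CTs, the stated maximum exposure should be about 17-19 rem rather than 12.3, with 56-64 background years rather than 41, cancer risk 1.6-1.9% rather than 1.2%, and fatal cancer 0.8-0.9% rather than 0.6%. That is 37-56% higher. The range rests on three assumptions: a biopsy dose between 0 and 1.5 times that of a CT, the protocol's own dose-to-risk conversion, and CT used at every assessment. It does not include confirmatory scans, post-treatment scans or treatment beyond two years.

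The gap arises only for participants still being scanned after week 62 or 64, and the documents do not say how many that will be. No endpoint, decision rule or sample size is affected. It is nonetheless a safety statement that errs on the favourable side and is cheap to correct, so it should be corrected.

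**What to change.** Reconcile section 12.4.1.5 with sections 3.1 and 3.5 (footnote 13). Recount the maximum number of CTs over the two-year treatment period, state which confirmatory and post-treatment scans are included, and recalculate dose, background equivalent and both risks from the actual per-procedure doses. If nine is meant to cover only certain scans or one year, say which, and give the full-study total beside it. Carry the change to any other document that repeats the figure.

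The cost is a recalculation and an amended paragraph. The stated risk becomes less favourable.

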12.4.1.6 Risks of MRI

People are at risk for injury from the MRI magnet if they have some kinds of metal in their body. It may be unsafe to have an MRI scan for participants with pacemakers or other implanted electrical devices, brain stimulators, some types of dental implants, aneurysm clips (metal clips on the wall of a large artery), metal prostheses (including metal pins and rods, heart valves, and cochlear implants), permanent eyeliner, tattoos, an implanted delivery pump, or shrapnel fragments. Welders and metal workers may have small metal fragments in the eye.

People with fear of confined spaces may become anxious during an MRI. Those with back problems may have back pain or discomfort from lying in the scanner. The noise from the scanner is loud enough to damage hearing, especially in people who already have hearing loss. There are no known long-term risks of MRI scans.

12.4.1.7 Risks of Gadolinium

The risks of an IV catheter include bleeding, infection, or inflammation of the skin and vein with pain and swelling.

Mild symptoms from gadolinium infusion occur in fewer than 1% of those who receive it and usually go away quickly. Mild symptoms may include coldness in the arm during the injection, a metallic taste, headache, and nausea. In an extremely small number, fewer than one in 300,000 people, more severe symptoms have been reported including shortness of breath, wheezing, hives, and lowering of blood pressure.

People with kidney disease are at risk for a serious reaction to gadolinium contrast called “nephrogenic systemic fibrosis (NSF)”. This condition always involves the skin and can also involve the muscles, joints and internal organs. NSF has resulted in a very small number of deaths.

Most of the gadolinium contrast leaves the body in the urine. However, the FDA has issued a safety alert that indicates small amounts of gadolinium may remain in the body for months to years. The long-term effects of the retained gadolinium are not known. Some types of gadolinium contrast drugs are less likely to remain in the body than others. The gadolinium contrast drugs that are less likely to remain in the body will be used on this study.

